#### (11) QOL indices (EQ-5D-5L, KDQOL)

The score of the QOL index should be calculated and provided by treatment group.

##### 1) EQ-5D-5L

The number, its proportion, and their two-sided 95% CI (Clopper-Pearson [Exact] method) of subjects in responses in 5 levels to the 5 questions (mobility, self care, usual activities, pain/discomfort, anxiety/depression) should be provided at each evaluation time point.

For Index value and VAS score, descriptive statistics of measured values and descriptive statistics of changes from the first day of the treatment period should be provided for each treatment group at each evaluation time point. A paired t-test should be performed for before and after comparison of changes from the first day of the treatment period.

A group comparison should be conducted for the changes in Index value and VAS score from the first day of the treatment period at each evaluation time point using the MMRM model (with compound symmetry [CS] for within-subject variance-covariance matrix). LSMean, its standard errors, and 2-sided 95% CI should be calculated, and the point estimate, its standard errors, 2-sided 95% CI, and p-value should be provided for the group difference (MT-6548 – darbepoetin) of the LSMean by treatment group.

The correlations of Hb value and Index Value, and Hb value and VAS score at all evaluation time points should be evaluated using linear regression and Emax model. For linear regression, the estimated items analyzed by the following model (Refer to “linear regression model”) should be output, and the p-value of the test with 0 slope as the null hypothesis should be calculated. Scatter plots and regression lines should be prepared separately for each treatment group. On the Emax model, estimated items (Refer to “Emax model”) analyzed by the following model should be output. Scatter plots and regression curves should be prepared separately for each treatment group.

[Linear regression model]

- ✓ Regression equation:  $Y = aX + b$
- ✓ X: Hb value or change in Hb value from the first day of the treatment period
- ✓ Y: Index value, VAS score, or change in index value or VAS score from the first day of the treatment period
- ✓ Estimated item (output item): a, slope of the regression line and its standard error; b, intercept of the regression line and its standard error; r, correlation coefficient

[Emax model]

- ✓ Model: 4-parameter logistic model
- ✓ X: Hb value
- ✓ Y: Index value or VAS score
- ✓ Estimated item (output item):  $EC_{50}$  with its standard errors and 2-sided 95% CI, Emax with its standard errors and 2-sided 95% CI, min with its standard errors and 2-sided 95% CI, slope with its standard errors and 2-sided 95% CI, R-Square (contribution ratio)

2) KDQOL

Descriptive statistics of KDQOL should be calculated in each treatment group by subscale (Section 4 [Table 4.16.2] “subscale”) for measured values and changes from the first day of the treatment period at each evaluation time point. Scores by subscale should be calculated using a scoring method 2) (Section 4.16).

A paired t-test should be performed for before and after comparison of changes in KDQOL from the first day of the treatment period.

A group comparison should be conducted for the change in KNDQOL from the first day of the treatment period at each evaluation time point. LSMean, its standard errors, and 2-sided 95% CI should be calculated, and the point estimate, its standard errors, 2-sided 95% CI, and p-value should be provided for the group difference (MT-6548 – darbepoetin) of the LSMean by

treatment group using the MMRM (with compound symmetry [CS] for within-subject variance-covariance matrix).

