Blood sampling and measurement will be performed for haematocrit and RBC count on the first day of the screening period, the first day of the treatment period, Weeks 2, 4, 6, 8, 10, 12, 16, 20, 24, 28, 32, 36, 40, 44, 48, and 52 of the treatment period, and the day of discontinuation of treatment.

(10) Reticulocytes (counts and fractions)

Blood sampling and measurement will be performed for reticulocytes (counts and fractions) on the first day of the screening period, the first day of the treatment period, Weeks 2, 4, 6, 8, 10, 12, 16, 20, 24, 28, 32, 36, 40, 44, 48, and 52 of the treatment period, and the day of discontinuation of treatment.

(11) EPO

Blood sampling and measurement of EPO will be performed on the first day of the treatment period, treatment period Weeks 2, 4, 6, 12, 24, 36, and 52, and the day of discontinuation of treatment. Blood sampling time will be recorded in CRFs.

EPO measurements will be disclosed to the sponsor after key code opening, but will not be disclosed to subjects, study center staff, or monitoring staff until completion of the final data

lock at the end of the study. Study centers are prohibited from measuring EPO during the treatment period in order to maintain blinding.

(12) QOL measures (EQ-5D-5L, KDQOL)

Subjects will fill out EQ-5D-5L and KDQOL questionnaires (Appendices 4 and 5) on the first day of the treatment period, treatment period Weeks 12, 24, and 52, and the day of discontinuation of treatment, and results recorded in CRFs.

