### 8.1 Basic matters

#### 8.1.1 Level of significance and confidence coefficient

When implementing tests, level of significance should be set at 2-sided 5%. Confidence interval will be 2-sided with a confidence coefficient of 95%.

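### Read naturally, the Hb versus EQ-5D regressions pool all visits into one fit per arm with no subject term, so their standard errors, slope p-values and Emax intervals ignore within-subject correlation

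*SAP*

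**What the plan says.** The analysis is in the final SAP, section 8.5.2 (11) 1) EQ-5D-5L. The Phase 1 SAP, section 8.5.3 (11) 1), has the same text, and the errata for the SAPs do not touch it.

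- **Data.** Hb is paired with the EQ-5D index value and with the VAS score "at all evaluation time points should be evaluated using linear regression and Emax model".
- **Linear model.** Y = aX + b, where X is "Hb value or change in Hb value from the first day of the treatment period" and Y is the index or VAS, or its change. The outputs are slope and intercept with standard errors and the correlation coefficient, and "the p-value of the test with 0 slope as the null hypothesis should be calculated".
- **Emax model.** A four-parameter logistic curve on raw values only. The outputs include "Emax with its standard errors and 2-sided 95% CI", and the same for EC50, the minimum and the slope.
- **Unit of fitting.** "Scatter plots and regression lines should be prepared separately for each treatment group", and likewise for the Emax curves. No split by visit is named.
- **Repeated measures.** Neither model names a subject effect, a within-subject covariance or a robust standard error.

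Protocol 9.2.3 (12) has the EQ-5D completed at baseline and at later visits (its list runs: "treatment period, treatment period Weeks 12, 24, and 52, and the day of discontinuation of treatment, and results recorded in CRFs"). A subject therefore has up to four scheduled EQ-5D assessments in the final analysis and three in Phase 1.

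**The concern.** Three features point to pooling. The by-visit analyses in the same subsection (response levels, descriptive statistics, group comparison) use the word *each*; only this one uses *all*. The SAP's other regressions fix a single visit or interval: Hb at Week 52 on CRP, mean dose over Weeks 48 to 52 on CRP, and ferritin at Week 52 on baseline ferritin. And the output list for this analysis carries no visit label.

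If visits are pooled, 150 subjects per arm supply up to 150 × 4 = 600 points that the ordinary formulae treat as independent. The SAP does not regard these scores as independent elsewhere: the paragraph before compares changes in the same scores with an "MMRM model (with compound symmetry [CS] for within-subject variance-covariance matrix".

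At stake is the error rate of a stated link between Hb and quality of life. Section 8.1.1 says that for tests the "level of significance should be set at 2-sided 5"%, with 95% confidence intervals. A slope p-value or an Emax interval built on understated standard errors would not carry those rates.

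**Working it through.** **The plan's own figure.** The documents state no power or precision for these regressions. The only power figure (above 95% for the primary endpoint, with 150 per arm, margin 0.75 and SD 1.73) reproduces at about 96.4% and has no bearing here.

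**Inputs.** From the documents: 150 subjects per arm; m = 4 EQ-5D visits for raw values in the final analysis and 3 in Phase 1; m = 3 and 2 post-baseline visits for change scores; two-sided 5%. Assumed, because the documents give no values: within-subject correlation 0.2 to 0.5 for Hb (r_x) and 0.5 to 0.7 for EQ-5D (r_y), exchangeable over visits, with every subject contributing all visits.

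**Formulae.** For a pooled simple regression with true slope 0, the ordinary formula understates the slope variance by the factor

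D = 1 + (m − 1) × r_x × r_y.

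The correct standard error is √D times the one reported, and the actual level of the nominal 5% test is 2 × [1 − Φ(1.96/√D)].

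**Raw values.**

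| Visits | r_x | r_y | D | √D | Actual level |
|---|---|---|---|---|---|
| 4 (final) | 0 | any | 1.00 | 1.00 | 5.0% |
| 4 (final) | 0.2 | 0.5 | 1 + 3 × 0.10 = 1.30 | 1.14 | 8.6% |
| 4 (final) | 0.3 | 0.7 | 1 + 3 × 0.21 = 1.63 | 1.28 | 12.5% |
| 4 (final) | 0.5 | 0.7 | 1 + 3 × 0.35 = 2.05 | 1.43 | 17.1% |
| 3 (Phase 1) | 0.2 | 0.5 | 1 + 2 × 0.10 = 1.20 | 1.10 | 7.4% |
| 3 (Phase 1) | 0.5 | 0.7 | 1 + 2 × 0.35 = 1.70 | 1.30 | 13.3% |

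**Change scores.** Under compound symmetry with variance σ² and correlation ρ, each change has variance 2σ²(1 − ρ). Two changes sharing a baseline have covariance σ²(1 − ρ). Their correlation is therefore 0.5 whatever ρ is, for Hb and EQ-5D alike.

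- Final, 3 post-baseline visits: D = 1 + 2 × 0.5 × 0.5 = 1.50, √D = 1.22, actual level about 11%.
- Phase 1, 2 post-baseline visits: D = 1 + 1 × 0.5 × 0.5 = 1.25, √D = 1.12, actual level about 8%.

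**Check by simulation** (150 subjects, 4 visits, true slope 0, 4,000 trials per setting). For raw values with r_y = 0.7, the ordinary test rejected in 4.9%, 10.9%, 13.4% and 17.8% of trials at r_x = 0, 0.2, 0.3 and 0.5; the formula gives 5.0%, 10.0%, 12.5% and 17.1%. Change scores at 3 post-baseline visits rejected in 10.4% to 11.8%, including when the raw correlations were zero. With subject-clustered standard errors, rejection was 4.6% to 6.1% in every setting.

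**Emax.** No calculation was made. The same dependence among points enters the fit, so ordinary standard errors and intervals for its parameters should err in the same direction, but the linear-slope factor does not measure by how much.

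**The case against.** The strongest reply is that pooling is inferred. A correlation evaluated at all time points could mean a fit at every visit, and preparing plots by treatment group does not exclude a further split by visit. The wording nearby is loose in other places: the ferritin/TSAT analysis, for example, borrows a baseline definition about iron use. One word may therefore carry less weight than it seems to. The lists of output tables and figures (sections 12 to 14 of each SAP) might settle the matter, but their content is not in the text available. This stands in part. A reader might infer that the SAP states pooling outright and is plainly wrong; it does not state it. With one fit per visit, the independence objection falls away. Pooling remains the more natural reading, and the text needs to say which is meant.

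Second, the raw-value figures depend on assumed correlations. Hb is titrated towards 10.0–12.0 g/dL, entry requires a mean of 9.5–12.0 g/dL, and post-baseline EQ-5D visits are 12 to 28 weeks apart, so a low within-subject Hb correlation is plausible. This also stands: the raw-value range is illustrative and falls to nothing at zero correlation. It does not rescue the change scores, where the shared baseline creates the correlation.

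Third, EQ-5D is among the other endpoints. Phase 1 SAP 8.5.4.7 calls the analyses of these exploratory, and no success rule rests on the Hb slope. That limits the consequence, but an exploratory label does not make a standard error correct.

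**Conclusion.** The point holds conditionally. If visits are pooled, as the text most naturally reads, the linear model's standard errors and slope p-value, and the Emax model's standard errors and 95% CIs, ignore within-subject correlation. The two models report different things: the linear model has p-values but no confidence intervals, and the Emax model the reverse.

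For raw values, the size rests on exchangeable correlations that the documents do not supply, and on complete visits. Change scores need only compound symmetry and complete visits.

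Two stronger readings are not supported. One is that the trial's conclusions on efficacy are at risk. The primary non-inferiority analysis is separate, and the treatment comparison of EQ-5D already models within-subject correlation. The other is that a false Hb and quality-of-life claim is likely. The documents attach no claim to this slope, and the chance of a false positive depends on unknown correlations. This is a minor correction to an exploratory analysis.

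**What to change.** State in both SAPs whether visits are pooled.

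- **If pooled:** keep Y = aX + b, but take the standard errors and slope p-value from a subject-clustered robust variance. Obtain the Emax standard errors and 95% CIs from a bootstrap that resamples subjects. Clustered errors leave the fitted line unchanged; a random subject intercept would also reweight within- and between-subject information and so move the slope.
- **If per-visit fits were intended:** replace *all* with *each* and output one labelled fit per visit and arm.

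The cost is a few lines of code and no new data. Under the assumptions above, reported standard errors become about 14% to 43% larger for raw values at four visits and 10% to 30% larger at three. For change scores they become about 22% larger (final) or 12% larger (Phase 1). If the change is made after data lock, Protocol 13.4 requires the reason to be documented and the results to be distinguished from the original plan.

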#### **8.5.4 Statistical issues**

##### **8.5.4.1 Adjustment for covariates**

In the analysis of efficacy, in order to consider the effect of the measurement value of the first day of the treatment period on the change of each measurement in the group comparison, the analysis by the MMRM model should be conducted using the measurement value of the first day of the treatment period as a covariate in the general analysis.

##### **8.5.4.2 Handling of dropout or missing data**

Provided in "7. Data handling."

##### **8.5.4.3 Interim analysis and data monitoring**

The statistical analysis plan for the fixed data for the treatment period phase 1 was prepared separately, and the statistical analysis was conducted. This statistical analysis plan was prepared to analyze the final fixed data.

##### **8.5.4.4 Multicenter trial**

For FAS, the following analysis should be conducted for each following endpoint for each facility. Descriptive statistics of Hb values should be calculated at Week 52 of the treatment period (imputed by the LOCF method) for each treatment group.

Descriptive statistics of mean dose of the study drug should be calculated for Week 48 to Week 52 of the treatment period for each treatment group.

##### **8.5.4.5 Subgroup analyses**

For the FAS, the following analyses should be performed for subgroups based on stratification factors (Table 8.5.4.5.1) for each of the following endpoints.

(1) Hb value at Week 52 of the treatment period

LSMean, standard error, and 2-sided 95% CI should be calculated for each treatment group using the MMRM model (with compound symmetry [CS] for within-subject variance-covariance matrix). The point estimate, its standard errors, 2-sided 95% CI, and p-value should be calculated for the between-group difference (MT-6548 – darbepoetin) of LSMean.

(2) Study drug mean dose at Week 48 to Week 52 of the treatment period

Descriptive statistics should be calculated for each treatment group.

(3) Target Hb achievement rate at Week 52 of the treatment period

The number, proportion, and 95% CI (Clopper-Pearson [Exact]) method) for the proportion of subjects with Hb values within the target range (10.0 g/dL to <12.0 g/dL) should be provided for each treatment group. The estimate, its 95% CI (exact method), and p-value (Fisher's exact test) for group difference (MT-6548 – darbepoetin) should be calculated.

Table 8.5.4.5.1 Subgroup analysis of efficacy

Endpoints	Stratification factor	Stratified category
1. Hb at Week 52 of the treatment period 2. Study drug mean dose at Week 48 to Week 52 of the treatment period 3. Target Hb achievement rate at Week 52 of the treatment period	Sex	Male, Female
	Age at time of consent (years)	<65, ≥65 <75, ≥75
	Dry weight (kg) on the first day of the treatment period	<60, ≥60
	Body mass index (kg/m  ) on the first day of the treatment period	<25, ≥25
	Underlying cause of CKD	Diabetes, hypertension, autoimmune/glomerulonephritis/vasculitis, interstitial nephritis/pyelonephritis, cystic/hereditary/congenital disease, neoplasm/tumor
	Duration of nephrogenic anemia (years)	<1, ≥1 to <5, ≥5
	Complication	hypertension, diabetes, dyslipidemia
	Hb value (g/dL) on the first day of the treatment period	<10, ≥10 to <11, ≥11
	Liver function test (U/L) on the first day of the treatment period	AST and ALT both not more than the upper limit of normal, either above the upper limit of normal and both ≤2 times the upper limit of normal, either >2 times the upper limit of normal
	CRP (mg/dL) on the first day of the treatment period	<0.31, ≥0.31
	Ferritin (ng/mL) on the first day of the treatment period	Divide the number of subjects into three categories based on the tertile
	TSAT (%) on the first day of the treatment period	Divide the number of subjects into three categories based on the tertile
	Smoking status	3 categories: never smoked, ex-smoker, current smoker

	Administration of oral iron supplement on the first day of the treatment period	Yes or No
	Treatment with oral iron supplement at Week 52 of the treatment period	Yes or No
	Iron-containing phosphate binders on the first day of the treatment period	Yes or No
	Iron-containing phosphate binders at Week 52 of the treatment period	Yes or No
	Previous ESA formulation	Epoetin alfa or epoetin beta, darbepoetin alfa, epoetin beta pegol, other
	Dosage of epoetin alfa, epoetin beta, or epoetin kappa	Divide the number of subjects into three categories based on the tertile
	Dosage of darbepoetin alfa	Divide the number of subjects into three categories based on the tertile
	Dosage of epoetin beta pegol	Divide the number of subjects into three categories based on the tertile
	CYP2B6 substrate*	Yes or No

\* List of CYP2B6 substrates obtained from the Metabolism and Transport Drug Interaction Database (DIDB®).

#### 8.5.4.6 Multiple comparison and multiplicity

The mean Hb values at Week 20 and Week 24 of the treatment period, the primary endpoints of this study, are evaluated in the analysis of the fixed data of the treatment period phase 1. There is no need to consider multiplicity in the analysis of the final fixed data.

#### 8.5.4.7 A study with active control intended to demonstrate equivalence

This is a non-inferiority study with an active control.

### 8.6 Safety analysis

The safety analysis set should be analyzed for each treatment group. When necessary, frequency and proportion should be calculated for discrete variables and descriptive statistics for continuous variables.

#### 8.6.1 Adverse events and adverse drug reactions

##### 8.6.1.1 Summary of adverse events and adverse drug reactions

The number (number of subjects with adverse events) and proportion of subjects in whom the following adverse events are observed at least once after the administration of the study drug to the end of the follow-up period should be calculated for each treatment group.

- Adverse event

- Adverse drug reaction
- Serious adverse event
- Serious adverse drug reaction
- Adverse event leading to discontinuation
- Adverse events leading to dose reduction or interruption of the study drug (active drug)
- Adverse events treated with rescue therapy
- Adverse event leading to death (adverse event of fatal outcome)

#### **8.6.1.2 Individual adverse events**

For adverse events, adverse drug reactions, serious adverse events, non-serious adverse events, serious adverse drug reactions, adverse events leading to discontinuation, adverse events leading to dose reduction or interruption of study drug, adverse events treated with rescue therapy, and adverse events leading to death, the number of subjects and incidence rate should be calculated for each adverse event classified by SOC and PT in MedDRA/J 20.1. (hereinafter, the same).

The SOC will be sorted by order of international consensus, the PT by descending order of the number of subjects with MT-6548 and by descending order of the number of subjects with darbepoetin (PT code ascending when the number is equal).

#### **8.6.1.3 Adverse events by severity**

The number of subjects and incidence rate should be calculated for adverse events and adverse drug reactions by severity for the overall and for individual events classified by SOC and PT.

The tabulation method by severity (severe, moderate, mild) is as follows.

- (1) When adverse events of different severity occur in the same subject, the most severe adverse event should be counted as 1 subject.
- (2) When multiple adverse events of the same severity occur in the same subject, the same severity should be counted as 1 subject.
- (3) When the same subject experienced the same adverse event multiple times, the most severe adverse event should be counted as 1 subject.

#### **8.6.1.4 Adverse event by time of onset**

The number and incidence rate of subjects with adverse events and adverse drug reactions should be calculated for adverse event and adverse drug reaction by time of onset (every 12 weeks) for the overall and for individual events classified by SOC and PT. For the calculation of the incidence rate, the number of subjects at each evaluation time point is used as the denominator.

\* The tabulation unit by time of onset should be as follows. However, if the same adverse event occurs in different categories in the same subject, it is counted as 1 subject in each category.

(Tabulation unit: from the first day of the treatment period [Day 1] to Day 84, Days 85–168, Days 169–252, Days 253–364, and after Day 365)

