### 8.2.2 Subjects who discontinued or interrupted their treatment

For subjects enrolled in the treatment period, the number and proportion of discontinued subjects should be tabulated in each treatment group and by reasons for discontinuation. Subjects who entered

specific comments ("Criterion for liver function") according to the input rules should be counted for the number of subjects discontinued by reasons that meet the discontinuation criteria for abnormal hepatic function values.

Items: Number and proportion of subjects who discontinued in each treatment group among those enrolled in the treatment period; number and proportion subjects who discontinued by reasons

In addition, for subjects enrolled in the treatment period, the number and proportion of discontinued subjects should be tabulated in each treatment group and in every 12 weeks (tabulation unit: from first day of the treatment period (Day 1) to Day 84, Days 85–168, Days 169–252, and Day 253 and onward.

Item: Number and proportion of subjects who discontinued in each treatment group among those enrolled in the treatment period

For subjects enrolled in the treatment period, the number of cases of interruption of MT-6548 tablets 150 mg in the MT-6548 group and darbepoetin alfa injection (recombinant) in the darbepoetin group should be tabulated by reasons for drug interruptions. The denominator of the proportion should be the sum of the number of drug interruptions. If there are multiple reasons for a single interruption, it should be counted for each reason and tabulated as the total number of interruption cases. For drug interruption due to abnormal hepatic function, subjects who entered specific comments according to the input rules ("Criterion for liver function") should be tabulated.

Items: Number of cases of interruption of MT-6548 tablets 150 mg/darbepoetin alfa injection in each treatment group among subjects enrolled in the treatment group; number and proportion of cases of interruptions by reasons

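### Two tables labelled as 12-weekly in the final-data SAP end in a 16-week bin with subject-count denominators, so a constant rate looks like a late rise within each arm

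*SAP*

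**What the plan says.** All SAP references are to the plan for the final data, not the separate plan for the Phase 1 data.

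**Adverse events (8.6.1.4).** The tabulation is "by time of onset (every 12 weeks) for the overall and for individual events classified by SOC and PT". The bins run "from the first day of the treatment period [Day 1] to Day 84", then "Days 85–168, Days 169–252, Days 253–364, and after Day 365". On the denominator: "the number of subjects at each evaluation time point is used as the denominator". On repeats: "if the same adverse event occurs in different categories in the same subject, it is counted as 1 subject in each category". So each cell is a number of subjects over a number of subjects.

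**Discontinuations (8.2.2).** These are to be shown "in each treatment group and in every 12 weeks". The bins after the first are "Days 85–168, Days 169–252, and Day 253 and onward", and the proportion is taken among all subjects enrolled in the treatment period, a denominator that does not change from bin to bin.

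Neither section mentions bin length, and the errata attached to the SAP do not touch either one. The neighbouring section 8.6.1.5 (events by dose immediately before onset) does divide by exposure time, in months of 30.4375 days. Section 8.6.1.6 (events by cumulative dosage) reports mean exposure days for each category. The onset table, whose axis is time, has neither.

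**The concern.** Fifty-two weeks is four 12-week periods plus 4 weeks, and both sections put the 4-week remainder into the last bin while keeping the 12-week description. A subject has a third more time in which to have an event or to discontinue in that bin than in any earlier one. With no adjustment, the last bin exceeds its neighbour even if nothing changes over time. A true 25% fall in the rate in that bin would look flat for uncommon events, because 0.75 × 112/84 = 1.

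Protocol sections 1(4) and 5.2 give long-term safety as the reason for treating to 52 weeks. A reader will use the onset table to judge whether events become more frequent with time on drug. The distortion runs in the same direction in every row, overall and by SOC and PT, and lies wholly within Phase 2.

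**Working it through.** **1. Bin widths** (end day − start day + 1, from 8.6.1.4):

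- Days 1–84: 84 days, 12 weeks
- Days 85–168: 84 days, 12 weeks
- Days 169–252: 84 days, 12 weeks
- Days 253–364: 112 days, 16 weeks

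The stated 12-week width reproduces for the first three bins and not for the fourth. The ratio is 112/84 = 1.33. In 8.2.2 the last bin is open. The Week 52 window in protocol Table 9.1-1 (Days 357–371) puts its length at about 15 to 17 weeks, nominally 16.

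**2. Adverse events under a constant hazard.** If p is the proportion with an event in 84 days, the proportion in 112 days is 1 − (1 − p)^(112/84). The documents give no event rates, so p is an assumed range.

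| 12-week bin (assumed) | Last bin | Ratio |
|---|---|---|
| 2% | 2.66% | 1.33 |
| 5% | 6.6% | 1.32 |
| 10% | 13.1% | 1.31 |
| 30% | 37.8% | 1.26 |
| 50% | 60.3% | 1.21 |
| 90% | 95.4% | 1.06 |

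Allowing dropout within the bin, with hazard d for dropout and l for the event, the proportion is l/(l + d) × (1 − exp(−(l + d)t)). With an assumed 10 to 30% dropout over 52 weeks, the ratio at p = 10% is 1.29 to 1.31, so little changes.

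The table assumes that every subject has the same hazard. If hazards vary between subjects the excess is smaller. With exponentially distributed hazards (an illustration) the proportion is 1 − 1/(1 + mt), where m is the mean hazard. A 12-week 50% means m × 84 = 1, and the last bin is 1 − 1/(1 + 4/3) = 57.1% rather than 60.3%.

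**3. Discontinuations under a constant hazard.** The denominator is fixed, so the formula in step 2 does not apply. With total dropout D by Day 364, S(t) = (1 − D)^(t/364), and each bin shows S(start) − S(end). D is assumed.

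| Total dropout | Bin 1 | Bin 2 | Bin 3 | Last bin | Last/third | Last/first |
|---|---|---|---|---|---|---|
| 10% | 2.4% | 2.3% | 2.3% | 3.0% | 1.30 | 1.24 |
| 20% | 5.0% | 4.8% | 4.5% | 5.7% | 1.26 | 1.13 |
| 30% | 7.9% | 7.3% | 6.7% | 8.1% | 1.21 | 1.03 |
| 40% | 11.1% | 9.9% | 8.8% | 10.2% | 1.16 | 0.92 |

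The last bin stops exceeding the first at about 33% total dropout, and stops exceeding the third at about 66%.

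**4. What a split alone would do.** With a cut at Day 336, Days 253–336 match the earlier adverse-event bins (ratio 1.00). The 28-day remainder then shows 1 − 0.9^(28/84) = 3.5% where the 12-week figure is 10%. For discontinuations at 20% dropout the row becomes 5.0, 4.8, 4.5, 4.3 and 1.4%. Without a rate or a label, a false rise has been exchanged for a false fall.

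**5. What a rate does.** Events divided by patient-months at risk are constant across bins of any width when the hazard is constant. If subjects rather than events are counted, each subject's time must stop at the first event in the bin. Dividing by the full bin would over-correct for common events: at 50%, (60.3/112)/(50/84) = 0.90.

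**The case against.** The strongest reply is that the comparison that matters is safe. Both arms use the same bins, so MT-6548 against darbepoetin within any bin has no bias from bin width, and a late effect specific to MT-6548 would still show against the concurrent blinded control. That stands. A reader might infer that these tables could create or hide a difference between the arms, or that the long-term safety objective is compromised. The documents support neither. That objective covers all 52 weeks, the whole-period adverse-event tables (SAP 8.6.1.1 to 8.6.1.3) serve it first, and tables by onset time are a descriptive addition to what protocol 13.3.3 asks for.

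It is also fair to say that the day limits are printed, that 52 is not a multiple of 12, and that both sections group the remainder in the same way. This looks like a consistent grouping with a loose label. But the label describes the bins wrongly, and most readers of an output table will take the description as given.

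A reader might also carry the one-third inflation over to discontinuations. That is not supported: the fixed denominator dampens the effect to about 1 point against the preceding bin at 20% dropout. Finally, cutting 8.2.2 at Day 336 and doing nothing else would mislead in the opposite direction. That objection is right and shapes the fix.

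**Conclusion.** The concern holds for the descriptive time trend within each arm, and only there. The last on-treatment bin is 16 weeks in a table described as 12-weekly, and no subject count corrects for the extra time at risk. The width ratio of 1.33 follows from the SAP alone. The incidences and dropout totals are assumptions, because the documents give none.

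The excess in the adverse-event table is at most 33% relative, for uncommon events. It is about 10 percentage points at a 12-week incidence of 50% if all subjects share one hazard, less if they do not, and only about 6% relative at 90%. In the discontinuation table it is smaller and depends on total dropout. Comparisons between arms within a bin, whole-period adverse-event totals and the primary analysis are not affected.

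A small related gap: read literally, the bin list in 8.6.1.4 leaves Day 365 unassigned, although the last bin was probably meant to start on that day.

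**What to change.** **8.6.1.4.** For every bin, add events (or subjects with a first event in the bin) per patient-month at risk in that bin, and define time at risk. Then either keep Days 253–364 and label it as 16 weeks, or split at Day 336 and label Days 337–364 as 4 weeks. Assign Day 365 explicitly. State what the subject count in the denominator means for a bin, since the present wording refers to a time point.

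**8.2.2.** Either label the last bin as Day 253 onward (about 16 weeks), or split at Day 336 and label the remainder as about 4 weeks. In both cases show discontinuations per patient-month at risk, so that no bin reads as a rise or a fall because of its width.

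**Cost.** No new data are needed, and study conduct and the primary analysis are unchanged. The work is one extra column per table and a new derivation of time at risk per calendar window, including the follow-up bin after Week 52. Section 8.6.1.5 supplies the month conversion but defines exposure by dose, so this derivation cannot simply be taken from there.
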